# 4.3 Postoperative only Treatment Group

This treatment group will be given the CyMedica Orthopedics e-vive system only upon discharge after surgery and will be asked to use the device as described in section 4.2.

### 5. ELIGIBILITY

#### 5.1. Inclusion Criteria

- 1. Patients undergoing unilateral primary total knee arthroplasty
- 2. Patients who are between the ages of 18 85 years
- 3. Patient has signed informed consent
- 4. Patient has access to a smartphone or tablet (Android or iOS)

### 5.2. Exclusion Criteria

- 1. BMI > 40
- 2. Inflammatory arthritis
- 3. Patients who are expected to be in extended care facilities after surgery
- 4. Patients who have used an at-home NMES device in the past
- 5. Preoperative daily use of narcotics (i.e., high tolerance)
- 6. Already enrolled in another research study, including the present study for contralateral knee
- 7. Other lower-extremity orthopaedic conditions which could interfere with limb function, especially those with significant pain requiring daily analgesic intake
- 8. Patients with concurrent abdominal, inguinal or femoral hernias
- 9. Cutaneous lesions in areas of electrode pad placement

- 10. Patients with a history of epilepsy
- 11. Patients with a cardiac pacemaker/defibrillator
- 12. Allergy to adhesives
- 13. Inability to meet follow-up visits required for the study
- 14. Patients who are a risk for poor compliance or have a poor understanding of the use of the NMES device
- 15. Condition deemed by physician or medical staff to be non-conducive to patient's ability to complete the study, or a potential risk to the patient's health and well-being

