### 3. HYPOTHESIS AND SPECIFIC AIMS

**Study Hypothesis:** Our hypothesis is that use of the CyMedica e-viveTM NMES both preop and postop can improve functional outcomes following TKA.

**Specific Aim 1.** Test whether patients treated with preop and postop NMES show improved physical performance measures when compared to postop only NMES group and standard of care group.

**Specific Aim 2.** Test whether patients treated with preop and postop NMES show improved patient-reported outcomes when compared to postop only NMES group and standard of care group.

**Specific Aim 3.** Test whether patients treated with NMES require fewer outpatient physical therapy visits when compared to the standard of care group.

**Specific Aim 4.** Test whether patients treated with NMES have a decreased discharge disposition to extended care facilities as well as shorter length of stay in extended care facilities compared to standard of care group.

**Specific Aim 5**. Test whether patients treated with NMES have decreased 90 day postoperative readmission rates compared to the standard of care group.

**Specific Aim 6.** Test whether patients treated with NMES have decreased dependence of the use of ambulatory assist devices.

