#### **Postoperative Assessments**

After surgery, one or more of the following will be collected through the online app and at follow-up visits.

- Device usage patterns (thru app)
- Range of motion of affected knee (thru app and at follow-up)
- TUG test
- Stair Climb test
- QFM strength
- Modified KOOS and VR-12 assessments
- VAS pain score

- Length of stay (hospital, extended care facility)
- 90 day readmission rate
- Discharge Disposition (home vs skilled nursing facility vs inpatient rehabilitation)
- Patient Satisfaction measures
- Any use of an ambulation assist aid
- Activity levels using Misfit Wearables® fitness monitor will be uploaded and incorporated into online app

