### 7. CLINICAL OUTCOMES

# 7.1. Sample Size Justification

A recent review paper written by Maddocks et al looked at eight different studies that used quadriceps muscle strength as an outcome and created a pooled analysis. They found a standardized mean difference of 0.90 for quadriceps muscle strength between control and NMES intervention groups. Sample size was calculated using this standardized mean difference, along with 80% power and the level of significance (p-value) set to 0.05. This study will require 20 patients per group. However, adding in a 10% expected dropout rate, planned enrollment will be 22 patients per group for a total enrollment of 66 patients.

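### Exclusion 3 leaves Aim 4 only unexpected facility discharges, too few for an informative test, and the facility-stay comparison rests on a subgroup selected after randomisation

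*Combined protocol and SAP*

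**What the plan says.** Specific Aim 4 in section 3 is to test whether patients treated with NMES have "decreased discharge disposition to extended care facilities as well as shorter length of stay in extended care facilities compared to standard of care group". Exclusion criterion 3 in section 5.2 removes "Patients who are expected to be in extended care facilities after surgery". Under sections 5.3 and 6.2 eligibility is checked at preoperative screening, before the randomisation envelope is opened and before any device use.

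Section 6.3 (Postoperative Assessments) still lists both outcomes: "Length of stay (hospital, extended care facility") and "Discharge Disposition (home vs skilled nursing facility vs inpatient rehabilitation"). Section 7.2 gives one rule for all outcomes: Student's t-test for means, Pearson chi-square for categorical variables, significance at p<=0.05, by assigned group. Section 7.1 sizes the trial for quadriceps strength alone. No event rate, power or separate analysis is given for Aim 4, and nothing limits the aim to patients expected to go home.

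On timing, section 4.2 resumes device use after discharge. Section 4.3 gives the postoperative-only arm its device at discharge, while section 5.4 also allows hand-out before surgery, with use to begin after surgery.

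**The concern.** The aim and the entry criterion pull against each other. The patients most likely to go to a facility are removed before NMES could change anything, so the aim as worded covers a population that the trial does not enrol. With few events left, a null disposition result could be taken as evidence that the device does not help, when the data could hardly have shown otherwise.

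The second half of Aim 4 has a different fault, which a larger trial would not cure. A facility stay exists only for patients admitted to a facility. Admission happens after randomisation, and the same aim expects NMES to reduce it. On the natural reading of section 7.2, a t-test would compare mean stay among those admitted. The admitted patients in the two groups need not be alike, so randomisation no longer protects the comparison.

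**Working it through.** **The plan's own figure.** Section 7.1 uses a "standardized mean difference of 0.90 for quadriceps muscle strength" with "80% power and the level of significance (p-value) set to 0.05". Two-sided, n per group = 2(1.960 + 0.842)²/0.90² = 19.4, so 20, as stated. Then 20 × 1.10 = 22 and 3 × 22 = 66, also as stated. These figures concern the primary endpoint only.

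**Inputs for Aim 4.** There are 22 control patients and 44 NMES patients (two arms of 22). Aim 4 speaks of patients treated with NMES, so both arms are pooled at first. The facility-discharge rate after exclusion 3 is an assumption: 2%, 5% or 10%.

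**Events needed if NMES prevents every facility discharge (0 of 44).** With x control events, Pearson X² = 66(44x)²/[x(66 − x)·22·44], against a critical value of 3.84.

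- x = 1: X² = 2.03, not significant. Fisher p = 0.333.
- x = 2: X² = 4.125, p = 0.042. Fisher p = 0.108.
- x = 3: Fisher p = 0.034.

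Pearson therefore needs 2 control events and Fisher needs 3. At x = 2 the smallest expected cell count is 2 × 22/66 = 0.67, far too small for the chi-square approximation to be trusted.

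**Chance of reaching that**, with X ~ Binomial(22, p):

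| Assumed rate | Expected control events (22p) | No control event, (1 − p)^22 | Pearson, P(X ≥ 2) | Fisher, P(X ≥ 3) |
|---|---|---|---|---|
| 2% | 0.4 | 64% | 7% | 1% |
| 5% | 1.1 | 32% | 30% | 9% |
| 10% | 2.2 | 10% | 66% | 38% |

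**A halving instead of complete prevention.** Enumerating all outcomes for 22 against 44 gives Pearson power of 5%, 11% and 13% at the three rates.

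**Role of sample size.** Suppose exclusion 3 were dropped and the control rate were 40% (again assumed). Pearson power for a halving would be 43% with 22 against 44, or 38% with 20 against 40.

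**Pooling.** Where the device starts at or after discharge, it cannot affect where the patient is discharged to. On the schedule in sections 4.2 and 4.3, only the combined arm, through its preoperative use, can inform disposition. For 22 against 22 with no NMES events, Pearson needs 4 control events (p = 0.036) and Fisher needs 5 (p = 0.048). The chance of at least 4 is 0.1%, 2% and 17% at the three rates.

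**Facility stay.** The number admitted across all arms is 66p = 1.3, 3.3 and 6.6 with no effect. With a halving it is 22p + 44p/2 = 44p = 0.9, 2.2 and 4.4.

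An invented example shows the selection problem. Take two arms of 22. Control has stays of 5, 10 and 21 days, a mean among those admitted of 36/3 = 12. NMES prevents the two shorter stays, so its mean is 21 and the device appears to lengthen stay. Counted over every randomised patient, control has 36/22 = 1.6 days and NMES has 21/22 = 0.95, which is the right direction.

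**The case against.** A reader might infer that Aim 4 cannot be tested at all. The documents do not support that. The criterion turns on expectation: patients expected to go home who are then sent to a facility stay in the trial, and section 6.3 records them. With complete prevention and a 10% rate, the planned test would succeed about two times in three.

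A reader might also blame a null result on the entry criteria alone. That goes too far as well. Section 7.1 sizes the trial for quadriceps strength, and power for a halving stays below 50% even at a 40% control rate without the exclusion.

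The Fisher figures do not describe the planned test, because section 7.2 names Pearson. They are shown only because the expected counts are so small.

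It is also fair to say that the rates are assumed, that the reversal example shows a bias is possible rather than likely, and that disposition and length of stay are of secondary interest under section 1.3. Adding hospital days to facility days would dilute an effect, since device use that starts at discharge cannot change hospital stay. All of this stands, and it limits the point to the wording and analysis of one secondary aim. It does not answer the selection problem in facility stay, which intention-to-treat grouping leaves untouched because patients who go home have no stay to compare.

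**Conclusion.** The conflict between exclusion 3 and Aim 4 is real and nothing in the documents reconciles it. Aim 4 can be run, but not informatively as stated: it reduces to unexpected facility discharge among patients expected to go home. With both NMES arms pooled and every event prevented, the chance of significance is 7% to 66% by Pearson over assumed rates of 2% to 10%; for a halving it is 5% to 13%. Pooling flatters these figures if the postoperative-only arm starts the device at or after discharge. Both the exclusion and the size of 66 are responsible, and the documents do not allow the share of each to be fixed, because they give no facility-discharge rate.

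The facility-stay fault does not depend on those rates. Comparing stay among admitted patients can mislead at any sample size; here it would also rest on about 1 to 7 patients. The primary endpoint and its sample size are unaffected.

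**What to change.** Keep exclusion 3 and bring Aim 4 into line with the enrolled population.

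1. Replace the facility-stay comparison with days in a facility counted for every randomised patient, with 0 if discharged home. Total hospital plus facility days may be added as an option. Both come from data already listed in section 6.3. This removes the selection problem but not the imprecision.
2. Restate the disposition part as unplanned facility discharge among patients expected to go home. Report counts with exact confidence intervals, label it exploratory, and claim neither a reduction nor the absence of an effect.
3. Show the combined and postoperative-only arms separately against control.
4. Reconcile sections 4.2, 4.3 and 5.4 on when the postoperative-only arm receives and starts the device, and state what this means for reading its disposition result.

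The cost is wording in section 3 and the analysis section, plus agreement among the three device-timing sections. No patients, visits or data items are added. The downside is that the sponsor gives up a confirmatory facility-discharge claim.

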# 5.3. Subject Identification

Patients scheduled for a unilateral primary TKA will be identified in EPIC or by ORIS. Those patients that meet the inclusion/exclusion criteria for the study will then be approached about the study in one of the following ways:

- 1. During a patient's clinical visit. Patients will be given of a copy of the Informed Consent to review.
- 2. By phone (see phone script). Those interested in participating in the study will be sent a copy of the Informed Consent by mail, and arrangements will be made to complete the consent process and OrthoMidas preoperative data collection during the patient's preoperative clinical visit just prior to surgery.

#### 5.4. Randomization

The patients will not be informed of their treatment assignment until a minimum of 4 weeks  $\pm$  7 days prior to day of surgery. A computer-based randomization generator (SAS, Inc.) will be used to assign patients into treatment arms in a 1:1:1 ratio, using a block randomization method. Patients in the combined treatment group will be given NMES units for device use beginning at at 4 weeks  $\pm$  7 days before surgery. Patients in the postoperative treatment only group will be given NMES units preoperatively and or upon discharge from the hospital. Those patients who are in the postoperative group only who receive the device preoperatively will be instructed to begin using the device only after their surgery. Patients in the control group will not receive any NMES units but will be given the option to crossover and receive a device at the end of the study.

### 6. STUDY PLAN

# 6.1. Patient Numbering

Each consecutive patient who presents at the study sites and in whom primary unilateral TKA is planned will be screened for inclusion into this study. Written informed consent must be obtained. Eligible patients will be assigned a unique study I.D. number for confidentiality and data collection purposes. Three-digit numbers will be assigned consecutively to each patient

starting at 001. A master list linking the subject to this unique study ID will be kept by the investigator only in a secure location.

#### **6.2.** Treatment Plan

Patients will be randomized to combined treatment group, postoperative NMES only group, or standard-of-care group. From 4 weeks  $\pm$  7 days before day of TKA, the patient will be evaluated until 12 weeks  $\pm$  1 week postoperatively.

# Preoperative Screening

Subjects who meet the inclusion criteria and exhibit no pre-operative exclusion criteria will receive a detailed explanation of the study and will be asked whether they are willing to participate in the study. If they agree to participate, written informed consent will be obtained.

The original consent form will be kept with the study records, and a copy of the consent will be given to the subject. A notation will be made in the subject's electronic medical record of participation in the study.

Pre-operative physical findings and a pertinent medical history will then be obtained and recorded on the appropriate case report forms.

Copies of all case report forms completed on subjects will be retained in individual subject files by the investigator in a secure location.

#### Preoperative Care

At 4 weeks  $\pm$  7 days prior to scheduled date of surgery, a randomization envelope will be opened indicating whether the patient is randomized into the combined treatment group, postoperative NMES only group, or the standard-of-care group. (See section 4 for more detail). Patients randomized to the combined treatment group will begin using the NMES device immediately until the day of surgery. Patients will be thoroughly educated on the use of the device at the time the patient receives the device. Patients may be given the device and educated by either physical therapists and or brace fitting specialists who are participating in the study. In addition, the study sponsor, Cymedica Orthopaedics will be available to provide technical support for the patient at any time if a device malfunction occurs. The study sponsor will not collect any information regarding the patient's status in the study, and will only know that the patient has a device but not which group they are in and or what phase of treatment is occurring. Patients will be asked to use the NMES device at the highest tolerable intensity. At the beginning of the study, all patients will be given an activity monitoring device made by Misfit Wearables®, which is similar to a Fitbit bracelet that they will wear daily. Activity levels will be uploaded and incorporated into online app. We will monitor for any changes in activity/ambulation among the groups to determine the effect of NMES usage on activity.

To ensure the validity of the NMES devices ability to achieve and deliver therapeutic doses in the NMES trial, the NMES device will be set at an intensity that has at least a minimal

therapeutic intensity level that each patient can tolerate. Due to the differences in body habitus as well as anatomic variances of motor nerve branch distributions which may both alter muscle response to electric current, this will be done for each individual patient that will be using the NMES device. Previous studies have determined that the level needed for the NMES device to deliver a therapeutic dose is based on an intensity that will elicit a quadriceps muscle contraction with either visual or palpable superior patellar glide[15–17]. During the patient's preoperative visit at the 4 week mark, each patient will be evaluated using the NMES device by designated trained research personnel who will determine the level of device intensity that is needed to cause superior patella glide, while ensuring the patient is able tolerate the intensity level. The intensity level will then be recorded and monitored through the device application. Patients will be instructed that they need to use the NMES device at least at the level that was determined to be therapeutic, but may increase the intensity as much as they can tolerate. To achieve maximum effective delivery of therapeutic NMES doses in static positions, we will have the patient place their leg that is going to be operated on in a recommended position between 60 to 75 degrees of knee flexion as much as possible while using the device. This will ensure the muscle will be stimulated near its optimal length-tension relationship to maximize the level of evoked force and muscle tension as well as minimizing patient discomfort and muscle fatigue associated with NMES use[15,18,19].

# Primary Unilateral TKA Procedure

At day of surgery (or 7 days prior to scheduled date of surgery), all patients will be evaluated as described previously. (See section 4 for more detail).

# Postoperative Care

Postoperative care will be standardized according to the protocol routinely used at our institution with rapid mobilization, gait training and range of motion [11]. Outpatient physical therapy will be scheduled as needed based on the therapist's assessment of recovery. Physical therapy locations must be Cleveland Clinic affiliated due to the need to use staff who have appropriate training on the NMES device usage to ensure accurate data collection. Pain will be controlled with orally administered long- and short-acting narcotics supplemented by parenteral narcotics as necessary. All study patients will receive standard of care anesthesia protocol.

Following discharge, patients will return for visits with a member of the research team at 3 weeks  $\pm$  7 days, 6 weeks  $\pm$  7 days, 12 weeks  $\pm$  7 days. Data will be collected and reported on the appropriate Case Report Forms at these follow-up visits.

As a last resort, if a patient is unable to keep one of these appointments, he/she will be either be mailed or emailed the OrthoMidas forms so the patient can fill them out. The patient will date and time the forms. They will then send the form back in a pre-addressed envelope. The patients email will be verified by the patient during a clinical visit to ensure accuracy of the correct recipient. Patients not responding to the initial mailer will be contacted by phone and forms may be administered over the phone. The mailers and/or phone calls will allow us to collect all data except the physical function measures. At the completion of the study, patients

will be given a voluntary survey about their experience with the clinical trial, which will be given in person, and or mail and email.

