#### 1.3 Outcome Assessments

These three groups will be analyzed using several outcome measures including validated patient-reported outcome measures the Knee Injury and Osteoarthritis Outcome Score(KOOS) [1], and Veterans RAND 12 item health survey (VR-12))[2], knee active range of motion (extension, flexion), quadriceps femoris muscle (QFM) strength, the Timed Up and Go Test [3] and the Stair Climb Test. The primary endpoint for the study is QFM strength. However, of secondary interest will be: 1) other physical performance measures (i.e. limb symmetry index and gait speed, activity levels), 2) Visual Analogue Scale (VAS) pain levels [4], on outpatient follow-up and immediately before & after NMES therapy, 3) length of stay, 4) Patient dependence on assistive device, 5) Patient satisfaction measures, 6) Patient discharge disposition, 7) Patient readmission rate. The proprietary app for this product will be used to track device usage (intensity, duration of session, frequency of use), knee range of motion and gait speed.

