# Usage and Compliance

The use time will be recorded by the device, which is capable of transmitting the information securely to an online application. The usage will be recorded from before surgery, and at the 3, 6, and 12 week visits in order to determine patient compliance with using the device. The acceptable minimum usage to be considered "compliant" with the protocol (for statistical analysis) are as follows:

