# **Operative Assessments**

The following will be collected from the Operative and Anesthesia Records and recorded on the appropriate pages of the CRF, and or Microsoft excel, Microsoft Word, and REDCap:

- Surgeon name
- Approach used
- Randomization assignment
- Diagnosis
- Length of surgery
- Estimated blood loss
- Type of anesthesia
- Implant type

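### The protocol does not require the person who measures quadriceps strength, the primary endpoint, to be unaware of treatment arm, and its visit and data arrangements make unblinding likely

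*Combined protocol and SAP*

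**What the plan says.** - **Endpoint.** Section 1.3: "The primary endpoint for the study is QFM strength". The schedule in section 1.4 has it measured at the 4-week preoperative visit, around the day of surgery, and at 3, 6 and 12 weeks. No test method, instructions or number of attempts is given.
- **Patients.** Section 5.4: "The patients will not be informed of their treatment assignment until a minimum of 4 weeks" before surgery, within a window. After that they know their arm. On controls: "Patients in the control group will not receive any NMES units". No sham is described, and section 4.1 offers controls the device at 12 weeks.
- **Visits.** Section 6.2, Postoperative Care: "patients will return for visits with a member of the research team at 3 weeks", then at 6 and 12 weeks. The team member is not specified further.
- **Usage.** Section 4.2, Usage and Compliance: "The usage will be recorded from before surgery, and at the 3, 6, and 12 week visits in order to determine patient compliance". The device captures the use time and can transmit it to an online application.
- **Assignment.** "Randomization assignment" is listed in section 6.3 under Operative Assessments, among items recorded on CRF pages, Excel, Word and REDCap. Under Confidentiality of the data, sharing is limited to study investigators and coordinators. No limit by role within that team is described.
- **Masking.** The only provision is in section 6.2, Preoperative Care, and concerns the sponsor, which "will only know that the patient has a device but not which group they are in".

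**The concern.** A strength measurement ordinarily depends on how hard the patient tries, and so on the instruction and encouragement given and the attempts allowed. That is a reading of what a strength test is, since the protocol describes no method. The missing method adds to the concern, because those elements are left to the tester. If the tester knows or guesses the arm and hopes the device works, small differences in coaching, repeat attempts or recording can move the primary endpoint toward NMES. Intention-to-treat analysis and the t-test in section 7.2 do not correct for this. At stake is whether a positive strength result can be attributed to the device.

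**Working it through.** **Step 1. Does anything keep the tester unaware of arm?**

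| Route to knowing the arm | What the protocol provides |
|---|---|
| Patient tells the tester | Patients know their arm; no instruction not to disclose it (5.4, 6.2) |
| Baseline visit | Baseline testing, envelope opening and intensity setting all fall at about 4 weeks before surgery; no order is stated (6.2, 6.3) |
| Usage recording | Takes place at the 3, 6 and 12 week visits; controls have no usage to record (4.2) |
| Assignment field | Recorded as study data; no role-based restriction within the team (6.3) |
| Device offer to controls | At 12 weeks, when the final strength test is due (4.1) |
| Masking rule | Sponsor only (6.2) |

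No section closes any of these routes for the strength tester. Equally, none says that the tester uses them. Unblinding is thus likely but not stated.

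**Step 2. Reproduce the plan's sample size.** Inputs from section 7.1: standardized difference 0.90, 80% power, significance level 0.05. Sidedness is not stated; two-sided is assumed.

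n per group = 2(1.960 + 0.842)² / 0.90² = 19.38, rounded up to 20, which matches the plan. Adding 10% gives 20 × 1.10 = 22 per group and 3 × 22 = 66 in total, also as stated. Blinding the tester does not change these numbers.

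**Step 3. Illustrate the effect of a biased measurement.** The documents give no bias size, so b = 0.1 to 0.4 SD in favour of NMES is an assumption. Others: no true effect, 20 per arm, one pairwise Student's t-test of an NMES arm against control, two-sided 0.05.

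- Degrees of freedom: 2 × 20 − 2 = 38; critical value 2.024.
- Smallest significant observed difference: 2.024 × √(2/20) = 0.64 SD.
- Noncentrality: b × √(20/2) = 3.162 b.
- Chance of a significant result favouring NMES: P(T > 2.024), with T noncentral t on 38 df.

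| Bias b (SD) | Noncentrality | Significant, favouring NMES | Significant, either direction |
|---|---|---|---|
| 0 | 0 | 2.5% | 5.0% |
| 0.1 | 0.316 | 4.9% | 6.1% |
| 0.2 | 0.632 | 9.0% | 9.5% |
| 0.3 | 0.949 | 15.0% | 15.2% |
| 0.4 | 1.265 | 23.4% | 23.4% |

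A bias of 0.2 SD is 0.2/0.90 = 22% of the planned effect. It multiplies the false-positive chance in favour of NMES by 9.0/2.5 = 3.6.

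**Step 4. Does the small sample make this worse?** No. The same 0.2 SD bias gives 9.0% at 20 per arm, 16.6% at 50 and 29.0% at 100. For a fixed bias the inflation grows with sample size.

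**The case against.** The strongest reply is that the protocol is silent about the tester, and silence does not show that the tester is unblinded. Much of this stands, and it limits the point in five ways.

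- **Knowledge of arm.** A reader might infer that the tester knows the arm. The documents do not identify the tester. Usage is captured by the device and app, and nothing says the tester handles it.
- **The CRF.** A reader might infer that strength is recorded on a form showing the assignment. The assignment is listed with the operative items, follow-up data go on whichever forms are appropriate, and the Postoperative Assessments list does not include it. What stands is only that no access limit within the team is stated.
- **Other performance tests.** A reader might extend the argument to the Timed Up and Go as a maximal-effort test. Appendix A asks for a comfortable, safe pace with one practice, so the argument fits it less well. The case here rests on strength.
- **Sample size.** A reader might infer that 20 per arm makes a small bias especially dangerous. Step 4 shows the reverse, and a 0.1 SD bias leaves about a 95% chance of no significant result favouring NMES.
- **The two NMES arms.** Aim 1 also compares combined with postoperative-only NMES. Both use the device after surgery, so postoperative usage recording does not by itself separate them. The illustration applies to NMES against control.

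The reply does not remove the omission. No section asks for a blinded tester, while the protocol did take the trouble to mask the sponsor, whose described role with patients is technical support.

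**Conclusion.** The concern holds as an omission with a likely consequence: nothing requires a blinded strength tester, and the arrangements make unblinding likely. The documents do not support the stronger claims that the tester knows the arm or records strength on a form that shows it.

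The range of 4.9% to 23.4%, against 2.5% without bias, is an illustration. It rests on an assumed bias of 0.1 to 0.4 SD, no true effect, 20 analysed per arm and a single two-sided comparison with control. It is not an estimate of the bias in this trial. The change is worth making because the bias cannot be removed in analysis and most of the remedy is a matter of ordering, access and wording.

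**What to change.** In sections 6.2 and 6.3:

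1. Complete baseline strength testing before the randomization envelope is opened. At every later visit, do strength and the other performance tests before any device or usage review.
2. Have them done by an existing team member who did not set the intensity or teach the device for that patient and is not told the arm. Ask patients not to disclose it.
3. Keep the assignment and usage data in REDCap forms that the tester cannot view, and out of any Excel or Word file the tester uses.
4. Write a strength-test procedure with the same scripted instructions and number of attempts in all arms.
5. State as a limitation that patients know their arm, so their own effort remains unblinded.

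**Cost.** Protocol wording, REDCap access settings and visit ordering; sample size and treatment are unchanged. Section 6.2 already involves several kinds of staff (therapists or brace-fitting specialists for teaching, designated personnel for intensity setting, team members for visits), so dividing the roles is plausible. The documents give no staffing numbers, so whether it fits the roster at each site needs checking. The ordering and access changes need no extra assessor. Some accidental disclosure will still occur.
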